| Title | Comfortable and Stabilizing Chin & Forehead Rest Attachment for Slit Lamp Configurations |
|---|---|
| Short Title | Invention Study |
| Brief Summary | Cohort will consist of 150 subjects consisting of those that are healthy or have an existing eye disease. Subjects will be imaged on two OCT devices: device N, invention attached to the device and device C, the standard conventional device. The Imager will time multiple durations, one of them which will act to evaluate the number of motion artifacts that arise due to both the instability and lack of comfort the patient is experiencing in that particular moment. Following the imaging session, subject will be asked which device was more comfortable. |
| Phase | NA |
| Objectives | The primary objective is to ascertain that the OCT Imaging device with the invention attached provides a more comfortable experience for the subject. While the secondary objective is to reduce the time it takes for the system to account for the number of motion artifacts. |
| Methodology | Randomized |
| Study Duration | Until target number of subjects is reached |
| Participant Duration | One clinic visit |
| Duration of IP administration | One clinic visit |
| Study Sites | NYU Department of Ophthalmology |
| Number of participants | 150 subjects |
| Description of Study Agent/Procedure | Comfortable chin and forehead rest that can be adjusted to fit each individual's size. |
| Statistical Analysis | Descriptive statistics for continuous variables and categorical data, presented using frequency counts and percentages will be used for group and device comparison. Patient experience will be assessed using two-sided exact test of proportion. Comfort levels of each device will be compared using t test. Linear mixed effect models will be utilized to compare the time duration while accounting for inter-eyes correlations. |

Version: 3.0

Schematic of Study Design

Screening Period

- Total n=150
- · Obtain informed consent
- Screen potential subjects by inclusion and exclusion criteria
- Obtain history, document

Day of Imaging

1. Randomize Order of Devices

 Provide clinic with 150 envelopes in which they are assigned with instructions regarding which device and eye the Imager should begin with (C/N & OS/OD)

2. Study Intervention

- Measure the length of the subject's face
- Provide subject with questionnaire containing the following
 - o Are you feeling well?
 - o Are you feeling tired today?
 - o Are you uncomfortable?
- Scans should be taken on device C and N on each eye

0

3. End of Study Assessments

- Directly following the imaging session, questionnaire including the following should be provided to the subject:
 - Which device was more comfortable?
 - o On a scale of 0-5, please rate the comfort level for each device

Version: 3.0

1 Key Roles

Ы

[name] [name] Department of Ophthalmology [name]

[contact]

[contact]

Clinical Research Program Manager

[name], CCRP

Department of Ophthalmology [name] [contact]

[contact]

Clinical Research Coordinator

[name]

Department of Ophthalmology [name] [contact]

[contact]

Research Ophthalmic Photographer

[name], OD

Department of Ophthalmology [name] [contact]

[contact]

Research Ophthalmic Photographer/Research Coordinator

[name]

Department of Ophthalmology [name] [contact]

[contact]

Sub-Investigator/ Device Engineer

[name], BS

Department of Ophthalmology [name] [contact]

[contact]

Statistician

[name]

Department of Ophthalmology [name] [contact]

[contact]

Version: 3.0

2 Introduction, Background Information and Scientific Rationale

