4.2 Study Endpoints

4.2.1 Primary Study Endpoints

Version: 3.0

In order to achieve the primary objective, proving that the level of comfort of the chin and forehead rest invention attached to the existing OCT imaging devices, as opposed to the conventional existing headframes is of a higher caliber, the primary endpoint will be achieved by providing the subject with a questionnaire directly after being imaged and asking two questions: which device, C/N, provided a more comfortable experience, and on a scale of 0-5 to rate the level of comfort, as a result of the headframe, i.e. chin and forehead rest, that the subject experienced while being imaged on either device C/N.

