6.1.6 Duration of Therapy

The duration of therapy includes one imaging session in which the subject is imaged on both device A and B for both eyes and has 1 scan of their Macula and 1 scan of their ONH acquired.

For the second objective, an evaluable participant should be consistent with Section 10, Statistical Considerations and/or Statistical Analysis Plan (SAP) which will include the minimum time duration it can take for an image to be acquired which can provide a result yielding in a statistically significant value.

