12.3 Informed Consent Process

12.3.1 Consent and Other Informational Documents Provided to Participants

Consent forms describing in detail the study agent, study procedures, and risks are given to the participant and written documentation of informed consent is required prior to starting intervention/administering study product.

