12.3.2 Consent Procedures and Documentation

Informed consent is a process that is initiated prior to the individual's agreeing to participate in the study and continues throughout the individual's study participation. Extensive discussion of risks and possible benefits of participation will be provided to the participants and their families. Consent forms will be IRB-approved and the participant will be asked to read and review the document. The investigator will explain the research study to the participant and answer any questions that may arise. All participants will receive a verbal explanation in terms suited to their comprehension of the purposes, procedures, and potential risks of the study and of their rights as research participants. Participants will have the opportunity to carefully review the written consent form and ask questions prior to signing. The participants should have the opportunity to discuss the study with their relatives or think about it prior to agreeing to participate. The participant will sign the informed consent document prior to any procedures being done specifically for the study. The participants may withdraw consent at any time throughout the course of the trial. A copy of the signed informed consent document will be given to the participants for their records. The rights and welfare of the participants will be protected by emphasizing to them that the quality of their medical care will not be adversely affected if they decline to participate in this study.

A copy of the signed informed consent document will be stored in the subject's research record. The consent process, including the name of the individual obtaining consent, will be thoroughly documented in the subject's research record. Any alteration to the standard consent process (e.g. use of a translator, , consent document presented orally, etc.) and the justification for such alteration will likewise be documented.

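### The primary endpoint is an unmasked report of comfort, the protocol's own wording favours the novel rest, and no stated safeguard limits expectation bias

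*Combined protocol and SAP*

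**What the plan says.** **Endpoint.** Section 4.2.1 rests the primary endpoint on two questions put to the subject directly after imaging: "which device, C/N, provided a more comfortable experience", and "on a scale of 0-5 to rate the level of comfort" for each device. The Schematic of Study Design words the first item as "Which device was more comfortable", without device letters. The List of Abbreviations defines C as conventional and N as novel.

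**Wording about the invention.** The Protocol Summary gives the title as "Comfortable and Stabilizing Chin & Forehead Rest Attachment for Slit Lamp Configurations", uses a short title that calls this a study of an invention, and describes the agent as "Comfortable chin and forehead rest that can be adjusted to fit each individual's size". Its objective is to establish that the invention is the more comfortable option. Section 3.1 is more neutral: it speaks only of assessing comfort.

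**What subjects are told first.** Section 12.3.1: "Consent forms describing in detail the study agent, study procedures, and risks are given to the participant". Section 12.3.2: "All participants will receive a verbal explanation in terms suited to their comprehension of the purposes, procedures, and potential risks of the study".

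**Safeguards.** Sections 2.3 and 6.1.5 randomise device order and first eye. The protocol does not describe masking of subject, Imager or analyst. It does not say who hands out the form, who is present while it is completed, or that subject-facing wording is to be neutral.

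**The concern.** Each subject uses both rests, sees and feels the difference, and then names a preference. An endpoint of this kind is open to expectation (the new rest should be better) and to courtesy (the staff would like it to be better). Both act in one direction, towards N. The staff around the subject may include the Imager and a sub-investigator who is the device engineer (Section 1), and Section 15 records that the PI has potential conflicts of interest, under a management plan that the protocol does not describe.

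Comfort preference is also the only endpoint with a sample-size calculation. If wording and setting push some subjects towards N, a significant result mixes real comfort with suggestion. Bias that enters at collection cannot be taken out in the analysis, and a larger sample makes a false conclusion more likely, not less.

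**Working it through.** **1. The plan's own figure.** Section 10.2 gives N=90, null proportion 50%, two-sided exact test at 0.05, and 80% power at P1 = 65.7%. The critical count r is the smallest with P(X ≥ r | n, 0.5) ≤ 0.025.

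- N=90: r = 55 (61.1%). Upper tail 2.23%, two-sided size 4.46%. Power at 65.7% is P(X ≥ 55 | 90, 0.657) = 84.8%, against the 80% stated. The plan's figure is on the cautious side, and nothing below depends on it.
- N=150, the enrolment target in the Protocol Summary and Section 5.6: r = 88 (58.7%). Upper tail 2.04%, two-sided size 4.09%.

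Both sizes are carried because Section 10.2 uses 90 and the enrolment sections use 150.

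**2. Why randomised order does not help.** Let d be an order effect favouring whichever rest comes second, and b a shift towards N from expectation. With no true difference:

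- N second: P(choose N) = 0.5 + d + b
- N first: P(choose N) = 0.5 − d + b
- Average over balanced order: 0.5 + b

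Order cancels d and leaves b untouched.

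**3. Illustration under a forced choice.** Assume no ties, a true split of 50:50, and a shift b. The documents give no value for b, so these are assumptions. If a share s of subjects name N from expectation and the rest split evenly, P1 = 0.5 + s/2, so b = s/2. The result is P(X ≥ r | n, 0.5 + b):

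| Shift b | Share s | N=90 (≥55) | N=150 (≥88) |
|---|---|---|---|
| 0 | 0% | 2.2% | 2.0% |
| 2.5 points | 5% | 6.2% | 7.6% |
| 5 points | 10% | 14.5% | 20.6% |
| 10 points | 20% | 46.0% | 66.3% |

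A share of (0.657 − 0.5) × 2 = 31.4% would by itself produce the design value of 65.7%.

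**4. The same calculation with ties counted against P1.** Section 10.2 defines P0 = 1 − P1 as the proportion reporting no difference. Assume, for illustration, that 20% report no difference and the rest split evenly. The baseline is then P1 = (1 − 0.20)/2 = 0.40.

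| Shift b | P1 | N=90 | N=150 |
|---|---|---|---|
| 5 points | 0.45 | 0.15% | 0.05% |
| 10 points | 0.50 | 2.2% | 2.0% |

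The direction of the bias is unchanged, but the false-positive rate stays at or below its nominal value over this range.

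**The case against.** The strongest objection is that the concern is about what subjects read and hear, and that text is not available. The questionnaire and recruitment script are separate attachments, and the consent pages are not in the review copy. Sections 12.3.1 and 12.3.2 are general consent language: they say that the agent and purposes are explained, not that subjects are told the rest is more comfortable. This stands. A reader might infer that subjects were told to expect comfort, but the documents support only that they are likely to be led that way.

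Two further inferences are tempting and should not be drawn:

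- That the preference item is put to subjects in terms of conventional and novel. Section 4.2.1 uses the letters C/N, but it is an endpoint description for protocol readers, and the schematic gives the item without letters.
- That Section 6.1.6 already adopts neutral coding where it says "the subject is imaged on both device A and B for both eyes". Those letters are not defined anywhere and conflict with C/N elsewhere. They are a labelling inconsistency, not a precedent.

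It is also fair to say that the shift sizes have no source, that the higher rates need a forced choice which Section 10.2 does not state, and that the hardware is visible, so neutral wording can remove only part of the bias. A letter key varied between subjects would mask nothing from someone looking at the rest, and one key error would reverse an answer. Finally, questionnaires are described as provided to the subject, which is compatible with self-completion.

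None of this supplies a safeguard. Self-completion is not the same as private completion, and the protocol requires neither.

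**Conclusion.** The concern holds as an unmitigated risk of bias, not as a contradiction in the plan or a demonstrated bias. The primary endpoint is subjective and unmasked, the protocol's title and agent description favour the invention, subjects learn about agent and purpose before answering, and no rule governs how the form is completed.

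The size is not known. Under a 50:50 forced choice, assumed shifts of 5 and 10 points raise the false-conclusion rate from about 2% to between 14.5% and 66.3%, depending on the shift and on whether N is 90 or 150. Under the Section 10.2 definition, with an assumed 20% reporting no difference, the same shifts give 0.05% to 2.2%. A reader might conclude that a significant result could never be told apart from a label effect. That is too strong, because it depends on the size of the shift and on how ties are counted, and the documents settle neither. The change is still worth making, because the bias acts in one direction on the only powered endpoint and the remedy is cheap.

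**What to change.** 1. Use a neutral study title and neutral wording in all subject-facing material (consent, recruitment script, questionnaire), for example *Comparison of two head supports for eye imaging*. Consent still states that one rest is investigational.
2. Identify the rests on the form by neutral, fixed descriptors, such as first and second rest used, and decode them from the recorded device order. Do not use conventional or novel.
3. Have the subject complete the form alone and seal it, out of view of the Imager, the PI and the device engineer. The Schedule of Events lists a survey after each imaging session, so the rule should cover both.
4. State residual expectation bias as a limitation of the primary endpoint, because the hardware cannot be masked.

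If the subject materials are already neutral, a sentence in the protocol confirming it meets item 1.

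**Cost.** One IRB modification, and linking each answer to the recorded device order. A wrongly recorded order would reverse that subject's answer, so the order should be recorded at the time of imaging and checked. No extra subjects or staff are needed.

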2.1 Background Information and Relevant Literature

Currently in Ophthalmological Offices, patients that are being imaged on OCT devices often do not have a comfortable patient experience. They tend to move away from the device in order to stretch every so often and oftentimes complain about it. This adds additional time to the imaging process, thereby extending the wait time for the following patients. Furthermore, due to the lack of ability to adjust the chin and forehead rest components to each individual patient's size, the patients tend to move around quite a bit which both lengthens the time, as previously mentioned, as well as increases the likelihood of artifacts, which lead to the misdiagnosis of Glaucoma. This is a catastrophic pitfall as 3 million Americans have Glaucoma, which is the "second leading cause of blindness worldwide. Additionally, there are 43 million people worldwide that suffer from blindness and 77% of those cases could have possibly been prevented by reducing the number of artifacts in their scans. To summarize, the purpose of this invention is to solve the problem in which patients are potentially being misdiagnosed or undiagnosed with ocular diseases as a result of patient discomfort induced movement and subsequent diagnostic testing artifacts which could prevent an efficient intervention to be enacted thereby reducing the patient's chances of suffering from a debilitating eye disease.

2.2 Name and Description of the Investigational Agent

The extendable and comfortable chin and forehead rest is a patent pending device (Atty. Dkt. No.: 046434-0793). The invention consists of six components: the chin rest, mount and its attachment and the forehead rest, mount and its corresponding attachment.

When designing this product, various constraints were considered: the need to easily and efficiently sterilize the components between patients, the material being biocompatible (in terms of it not having any adverse effects on the patient due to its properties), the materials selected and structure designed needed to prove to be durable enough to withstand the weight of a person's head, aid in providing the patient with a comfortable resting position, and, lastly, to stabilize the patient's head properly.

Table 1 shown below provides the Bill of Materials for the Chin rest. It includes the material used, quantity along with a description of the component.

| Part | Qty. | Description | Material |
|----------------------|------|------------------------------|------------------------|
| Chin rest Base Front | 1 | patient rests chin on | ABS/ Biomed Back Resin |
| Chin rest Base Back | | - | Steel Steel |
| Rotary Shaft | 2 | extension mechanism | 316 Stainless Steel |
| Bearing | 4 | reduces friction along shaft | 841 Bronze |
| Head Thumb Screw | 2 | locking mechanism | Steel low profile |

Version: 3.0

Table 1: Chin Rest - Bill of Materials

The mechanism used to adjust the chin rest for each individual patient are two rotary shafts that the chin rest can slide along to be extended as needed and locked in place by two head thumb screws (this design can be upgraded to operate via a remote control). Four bearings are also incorporated into the design in order to reduce friction caused by the movement of the shafts within the extrusions.

Lastly, a cushion is used for the rests, which provides the essential component of comfort enhancing the patient's overall experience.

In order to incorporate the chin rest into the existing ophthalmic devices on the market, a mount and attachment were designed. The mount functions as a stage for the chin rest and can be adjusted, by use of grippers, to fit the variable length of the chin rest for each patient's appropriate dimensions. The mount is then connected to the attachment via a ball joint. This provides the ability to make additional adjustments per patient as it can move in the y and z directions as well, which will ultimately maximize the stability of the patient's head while being imaged, as well as provide a more comfortable and positive patient experience. Finally, in order to connect the chin rest and mount to the devices, a simple clamping mechanism is utilized, which is designed for each device.

| In Table 2 below, the bill o | f materials is 1 | provided for the | the mount and | attachment fo | or the chin rest. |
|------------------------------|------------------|------------------|---------------|---------------|-------------------|
| | | | | | |

| Part | Qty. | Description | Material |
|---------------------|------|---|-----------------|
| Clamp (male) | 1 | half of clamp (specific to each device) | ABS |
| Clamp (female) | 1 | half of clamp (specific to each device) | ABS |
| Lock - Threaded Rod | 1 | locking mechanism for attachment to device | Stainless Steel |
| Slide Lock | 1 | locking mechanism for extending the mount | Stainless Steel |
| Threaded Pin | 1 | connects male and female clamp | Stainless Steel |
| Edge Adjuster | 4 | adjusts mount size according to chin rest extension | ABS |

Table 2: Mount & Attachment - Bill of Materials

The overall mass and weight of the chin rest, mount and attachment is approximately .249 kg and 2.44 N.

The forehead rest component of the invention was designed with similar considerations and constraints in mind. One additional constraint when designing the adjusting mechanism for different size patient heads was to ensure that while adjusting the forehead rest no part of the patient's skin on their forehead would be pinched as a result of the movement of the parts relative to one another.

Version: 3.0

The overall design of the forehead rest includes multiple mechanisms. Specifically, two mechanisms that are present to adjust for each patient include:

- 1) the cylinders protruding from the side of the forehead rest
- 2) the quick release strap on the buckle located on the front and center of the forehead rest. The cylinders are designed to fit into a slot clamped to the ophthalmic device and have a dual purpose in which it is used to account for adjustments needed to move the patient relative to the device, as well as mounting the forehead rest to the ophthalmic devices. Similarly, the quick release buckle is used to account for each individual patient's head size which can be done by tightening or loosening the strap accordingly. As the forehead rest is composed of the male and female parts, the male part would have the ability to move linearly relative to the female part.

The forehead rest would be made almost exclusively from ABS, not accounting for the parts sourced off the shelf (quick release buckle, screws, etc.) and the silicone cushion covering.

2.2.1 Preclinical Data

There is no available preclinical research data on the investigational product.

2.2.2 Clinical Data to Date

There is no available clinical research data to date on the investigational product.

2.3 Rationale

This study primarily focuses on increasing the comfort for each patient's experience as well as reducing motion artifacts by improving the former, as well as stabilizing the patient's head, accomplished by adjusting the chin and forehead rest for each individual patient. The cohort will consist of a total of 90 subjects consisting of subjects that are both healthy and have an existing eye disease, as commonly observed in ophthalmology outpatient offices.

In order for certain limitations to not affect the validity of the results, various aspects of the trial will be randomized. This includes, but is not limited to, the order in which a patient will begin being imaged on either device C/N and which eye, OS/OD the Imager will scan first. This can help account for parameters including whether the time it takes to image the patient and/or level of comfort is affected as a result of their degree of alertness, energy level, how they are feeling on that particular day, etc.

2.4 Potential Risks & Benefits

2.4.1 Known Potential Risks and Benefits

There is a risk of blurred vision and difficulty in near vision operation (e.g., reading and writing), which is common, due to the use of the dilating drops Phenylephrine Hydrochloride or Tropicamide. The effects of these drops will disappear within 3-4 hours after instillation. The participant may be asked to remain in the clinic in the event that they experience blurred vision and do not have an accompanying person.

Pupil dilation may cause an increase in eye pressure or the possibility of an angle-closure event,

Version: 3.0

which happens in a rare configuration of the eyes. All subjects will be examined clinically Before dilating drops are instilled to identify eyes at risk, in which case no dilation drops will be used. If either of these risks should occur, the subject will be treated immediately with eye drops at no cost.

Ophthalmologic OCT imaging is performed in a non-contact fashion, so there is minimal risk of infection to the participant. To reduce the possibility of eye infection, all exposed surfaces near the eye, as well as the chin rest and forehead rest of the instrument, will be cleaned with alcohol before participants are examined. The risk of infection is low.

Imaging will be performed using commercial (FDA approved) and non-commercial (non-FDA approved) OCT imaging instruments. All devices are subject to standard medical regulatory and safety requirements and adhere to the American National Standards Institute safety standards for the use and exposure to lasers. There is no known cumulative risk for repeating OCT scans multiple times on the same day or on different days.

Participants will receive no direct benefit by participating in this study. However, there may be societal benefit related to generalizable knowledge gained by doing this study.

3 Objectives and Purpose

